8.12 Notification to Authorities

The following events are generally considered reportable during the course of this study and should be reported to the sponsor within 24 hours of the time the Site learns of the event:

- any ADE, SADE, SAE, or USADE
- any Investigational Medical Device Deficiency that might have led to an SADE if
 - a) suitable action had not been taken or
 - b) intervention had not been made or
 - c) if circumstances had been less fortunate
- new findings/updates in relation to already reported events.

Events will be reviewed by Covidien or designee and will be reported to comply with local standards and mandatory reporting practices.

9.0 Device Deficiencies

A Device deficiency is an inadequacy of a medical device related to its identity, quality, durability, reliability, safety, or performance, such as malfunction, misuse or use error and inadequate labeling.

All Emprint™ Ablation System device deficiencies will be documented on the appropriate Device deficiency eCRF and the device should be returned to Covidien for analysis, if possible. Instructions for returning the device will be provided. Device deficiencies should also be documented in the subject's medical record.

Device deficiencies are NOT to be reported as AEs. However, if there is an AE that results from a device deficiency, that specific event would be recorded on the appropriate eCRF.

10.0 Safety Committees

The sponsor will employ a comprehensive safety plan for this study comprised of the following components:

10.1 Independent Medical Monitor

The Sponsor will utilize an Independent Medical Monitor to provide an independent medical review and adjudication of pre-specified adverse events in support of protocol defined endpoint data. The Independent Medical Monitor is a qualified, board-certified Interventional Radiologist. Refer to the Independent Medical Monitor charter for additional details.

11.0 Steering Committee

The Steering Committee will consist of the Principal Investigator at each clinical site as well as appropriate members of Covidien Clinical and Medical Affairs. The role of the steering committee is to make recommendations on the design and conduct of the study, the analysis of data, and the communication of results in alignment with the Covidien Publication and Authorship Policy.

12.0 Compliance

12.1 Statement of Compliance

This clinical investigation will be conducted in accordance with the ethical principles that have their origin in the Declaration of Helsinki, Clinical investigation of medical devices for human subjects — ISO 14155:2011 Good Clinical Practice, and any regional or national regulations, as appropriate.

The clinical investigation will not begin until all necessary approvals/favorable opinions are obtained from the appropriate IRB or IEC or regulatory authority, as appropriate. Should an IRB or IEC or regulatory authority impose any additional requirements, they will be followed.

Information regarding the study and study data will be made available via publication on clintrials.gov. Additionally, the results of this study will be offered for publication at the conclusion of the study, if participating investigators believe the data warrants publication in an appropriate journal.

12.2 Protocol Compliance

No changes to the protocol will be permitted without the written approval from Covidien and the IRB/EC. The investigator must notify Covidien and the reviewing IRB/EC of any deviation from the Investigational Plan when specific to the protection of the life or physical well-being of a subject in an emergency. Such notice must be given as soon as possible, but in no event later than 5 working days after the emergency has occurred. Except in such an emergency, prior written approval by Covidien is required for changes in or deviations from the Plan. If these changes or deviations affect the scientific soundness of the Plan or the rights, safety, or welfare of human subjects the IRB/EC will also be notified. All other deviations will be reported per the site's IRB/EC deviation policy. Should any deviations from the Investigational Plan occur, these

will be reviewed by Covidien for their clinical significance. If the event is performed without written approval from all parties, the investigator may be terminated from the study.

13.1 Monitoring Procedures

Site visits will be conducted by an authorized Covidien representative to inspect study data, subjects' medical records, and eCRFs in accordance with ISO 14155:2011 Good Clinical Practices and the respective local and national government regulations and guidelines (if applicable). The Study Investigator and the investigating site will permit authorized clinical research personnel and clinical monitors from Covidien and/or designee(s) employed by Covidien to review completed eCRFs, IEC or IRB decisions, and Investigator, clinical site records, and facilities relevant to this study at regular intervals throughout the study per the monitoring plan. Additionally, subject charts and clinical records will be requested and reviewed so that protocol adherence and source documentation can be verified. The accuracy and quality of the data obtained from the investigator and maintained by Covidien will be confirmed through a structured program of clinical field auditing and internal review detailed in the monitoring plan. In instances where data protection regulations prohibit the direct examination of hospital records by the study Sponsor or designee(s), the Investigator will cooperate in a system of source data verification with the Sponsor. Monitoring may be performed with in person visits or remotely, when applicable.

To ensure the rights, safety, and welfare of study subjects are being maintained, the monitor will review training records to ensure all study staff are trained on the study protocol and use of the study devices. If the monitor discovers that an investigator is not complying with the signed Investigator Agreement, the investigational plan, applicable laws, or any conditions of approval imposed by the reviewing IEC or IRB the monitor will report to the Sponsor and take such steps necessary to promptly secure compliance. If compliance cannot be secured, device shipments to the investigator may be discontinued and the investigator's participation in the investigation terminated. The monitor shall also require such an investigator to dispose of or return the device, unless this action would jeopardize the rights, safety, or welfare of a subject.

13.2 Data Collection and Processing

This study will utilize an electronic database and eCRF. In order to accurately collect all information, subject worksheets will be provided for study specific data (specific operative data points, etc.) not found in the medical records and will be considered the source document. All data requested on the eCRF are considered required. Data points not collected and/or recorded will be considered deviations unless otherwise specified. The Principal Investigator must ensure the accuracy and completeness of the recorded data and then provide his/her electronic signature on the appropriate eCRFs. The Investigator's electronic signature for specific eCRFs will be documented in compliance with local regulations. Changes to data previously submitted to the sponsor will require a new electronic signature by the Investigator to acknowledge/approve the changes.

Visual and/or computer data review will be performed to identify possible data discrepancies. Manual and/or automatic queries will be created in LiveTrial (RDC) system and will be issued to

the site for appropriate response. The site staff will be responsible for resolving all queries in the database.

14.0 Study Supplies and Device Accountability

14.1 Emprint™ Ablation System

The Emprint™ Ablation System will be provided to each site upon Sponsor collection and approval of all required regulatory documentation. The device will be labeled “Exclusively for Clinical Investigations” and should be stored in a secure (locked) area under the appropriate storage conditions. Access should be limited to designated study staff only. Device accountability logs will be provided to the site. It is the site’s responsibility to document the receipt (maintain shipping logs), disposition of the product (per subject use, including amount used, amount remaining, etc.), transfer (if applicable) and return of all unopened study devices.

14.2 Planning Laptop

A laptop loaded with the ablation planning application software will be provided prior to the start of the study. It is the site’s responsibility to record the serial number of the laptop upon receipt. Access to and use of the planning laptop should be limited to designated study staff only. Once the study has concluded, the planning laptop will be returned to Covidien.

15.3 Retention of Records

The investigator will maintain the records of the study including all pertinent correspondence, the study protocol with any/all amendments, all correspondence with and approval from the IEC, the clinical trial agreement, the Investigator Agreement, investigational device accountability records, individual subject records, and signed informed consent forms. Subject files and other source data must be kept for a period of not less than 2 years after the date on which this investigation is terminated or completed. Records may need to be maintained by the Principal Investigator for a longer duration if national regulations require or if agreed to in writing with Covidien. All data and documents should be made available if requested by relevant authorities.

15.4 Study Completion/Termination of Study

Covidien reserves the right to discontinue the study at any stage, with suitable written notice to all investigators, all reviewing IRBs or IECs, and FDA or Competent Authorities. Similarly, investigators may withdraw from the study at any time, subject to providing written notification to Covidien 30 days prior to the date they intend to withdraw. However, Covidien and investigators will be bound by their obligation to complete the follow-up of subjects already participating in the study. The subjects must be followed according to the clinical protocol, and information obtained during subject follow-up shall be reported to Covidien on the appropriate eCRF.

16.0 Appendices

There are no appendices to this protocol.

**Confidential**

## 1. Version History

Version	Summary of Changes	Author(s)/Title
1.0	
 
Initial Document Release
 
	[name], Principal Statistician
2.0	
 
Revise and reformat based on new SOP
 
	[name], Principal Statistician
3.0	
 
Redacted proprietary information to post with results on CT.gov in accordance with Final Rule
 
	[name], Clinical Research Coordinator III

## 2. List of Abbreviations and Definitions of Terms

Abbreviation	Definition
ADE	Adverse Device Effect; Adverse event related to the use of an investigational medical device, including adverse events resulting from insufficient or inadequate instructions for use, deployment, implantation, installation, or operation, or any malfunction of the investigational medical device, as well as any event resulting from use error or from intentional misuse of the investigational medical device.
AE	Adverse event; Any untoward medical occurrence, unintended disease or injury, or untoward clinical signs (including abnormal laboratory findings) in subjects, users or other persons, whether or not related to the investigational device. This includes events related to the investigational device or the comparator and procedures involved.
ASADE	Anticipated serious adverse device effect; an effect which by its nature, incidence, severity, or outcome has been identified in the risk analysis report (R0042262).
CIP	clinical investigational plan
CRF	Case report form
CT	computed tomography
Device deficiency	Inadequacy of a medical device related to its identity, quality, durability, reliability, safety, or performance, such as malfunction, misuse or use error and inadequate labeling.
EC	Ethics committee (see IEC)

This document is electronically controlled. Printed copies are considered uncontrolled.

**Confidential**

eCRF	Electronic case report form
H&E	Hematoxylin and eosin stain routinely used to evaluate the structural integrity of cells
IEC	Institutional ethics committee (see EC)
IFU	Instructions for Use; a manual or document accompanying a technical device that describes the directions by which the device should be used, applied, etc.
Investigative Site	An approved, participating study center/institution
Investigator	Either a principal, coordinating or sub-investigator, unless otherwise specified
IRB	Institutional Review Board
MWA	microwave ablation
NADH	$\beta$ -nicotinamide adenine dinucleotide, reduced; assay used to determine cell viability
OR	Operating Room
RDC	Remote data capture; internet-based data entry system used to enter and store study data points
RTP	remote temperature probe
SADE	Serious adverse device effect; adverse device effect that has resulted in any of the consequences characteristic of a serious adverse event
SAE	
Serious adverse event; an adverse event that
 
 
a) led to death,
 
b) led to serious deterioration in the health of the subject, that either resulted in 
 
1) a life-threatening illness or injury, or
 
2) a permanent impairment of a body structure or a body function, or
 
3) in-patient or prolonged hospitalization, or
 
4) medical or surgical intervention to prevent life-threatening illness or injury or permanent impairment to a body structure or a body function,
 
 
 
c) led to fetal distress, fetal death or a congenital abnormality or birth defect
 
 
NOTE: Planned hospitalization for a pre-existing condition, or a procedure required by the clinical investigational plan, without serious deterioration in health, is not considered a serious adverse event.

This document is electronically controlled. Printed copies are considered uncontrolled.

**Confidential**

TEAE	Treatment-emergent adverse event; any event not present prior to the initiation of the treatments or any event already present that worsens in either intensity or frequency following exposure to the treatments.
USADE	Unanticipated serious adverse device effect; serious adverse device effect which by its nature, incidence, severity or outcome has not been identified in the current version of the risk analysis report.

### 3. Introduction

The EMPRESS study is a post market prospective, non-randomized, single-arm, multicenter study, designed to demonstrate dose response of the Emprint™ Ablation System using a percutaneous approach in patients with metastatic or primary lung tumors.

This document provides a detailed description of the statistical methods and procedures to be implemented during the analysis of the study.

The proposed methods and approaches to the data analysis should be viewed as flexible if the data suggest and warrant deviations from this plan. However, any deviations from this analysis plan must be substantiated by a sound statistical rationale and documented in the final clinical study report. This statistical analysis plan (SAP) is based on version 2 of the protocol dated February 24, 2015.

### 4. Study Objectives

The primary objective of this post-market clinical study is to demonstrate technical performance of a CT-guided percutaneous microwave ablation system in patients with metastatic lung tumors or recurrent primary lung tumors.

Following CT-guided ablation of the tumor, a CT image will be performed to evaluate dose response. The ablation zone will then be resected as part of the standard surgical procedure and the tissue specimen will be examined using histology to determine the completeness of tumor ablation.

### 5. Investigation Plan

This will be a post market prospective, non-randomized, single-arm, multicenter study.

Ablations will be carried out using a percutaneous approach at a dose (power and time setting) selected during procedure planning. The procedure planning application will be used as an adjunct planning tool. While the physician prescribes the dose, the Emprint™ Procedure Planning Application overlays the 3-dimensional predicted ablation zone on the patient CT images, facilitating visualization of the predicted ablation zone relative to the target tumor. Once the ablation procedure is complete, the scheduled surgical tumor resection will be performed.

### 6. Determination of Sample Size

No formal sample size estimates were conducted for this post-market, prospective, non-randomized,

This document is electronically controlled. Printed copies are considered uncontrolled.

**Confidential**

single-arm, multicenter study. Up to 30 subjects who are scheduled for resection of metastatic or primary lung tumor(s) will be enrolled. Ablations will be carried out using a percutaneous approach at a dose (power and time setting) selected during procedure planning. Up to 10 study sites in the United States and Europe will participate in this trial.

## **7. Statistical Methods**

### **7.1. Study Subjects**

#### **7.1.1. Disposition of Subjects**

Subject disposition (e.g., number completing the study, number lost-to-follow-up) will be summarized with frequency tables. The following information will be provided by study site:

- Number and percentage of screen failures
- Number and percentage of enrolled subjects
- Number and percentage of subjects who have completed the Emprint™ ablation procedure
- Number and percentage of subjects who have completed the Emprint™ ablation procedure and the Primary Endpoint
- Number and percentage of subjects who have completed the Emprint™ ablation procedure and the Secondary Endpoint
- Number and percentage of subjects who have completed the postoperative evaluation / end of study Visit
- Number and percentage of subjects who exited the study, overall and by study exit type

#### **7.1.2. Clinical Investigation Plan (CIP) Deviations**

A CIP deviation is defined as an event where the Investigator or study personnel did not conduct the study according to the CIP. Deviations shall be reported regardless of whether medically justifiable or taken to protect the Subject in an emergency.

Except a change that is intended to eliminate an immediate hazard to a Subject, the protocol will be followed as described. Subject specific deviations and non-Subject specific deviations will be reported. Investigators will also adhere to procedures for reporting study deviations to their IRB in accordance with their specific IRB reporting policies and procedures.

#### **7.1.3. Analysis Sets**

In general, data analysis will be conducted on all subjects who are enrolled in the trial and undergo the ablation procedure using the Emprint™ system.

Intent-To-Treat (ITT): subjects enrolled into the study.

Modified ITT (MITT): ITT subjects who completed the ablation procedure. If all ITT subjects completed the ablation procedure, then the ITT population is the same as the MITT population.

Additional analysis sub-populations may be defined per scientific research need.

This document is electronically controlled. Printed copies are considered uncontrolled.

**Confidential**

## **7.2. General Methodology**

Descriptive statistics will be generated for pre-intervention demographics, procedural characteristics, and follow-up data collected. Categorical variables will be analyzed using frequency, incidence, and event rate. For continuous variables collected in the study, data will be summarized using mean, median, standard deviation, and range.

## **7.3. Center Pooling**

This is a multi-center clinical study, with standardization of subject enrollment, data entry and adverse event reporting. All investigational sites will follow the requirements of a common protocol, data collection procedures and forms. 30 subjects will be enrolled from up to 10 clinical sites, all the data will be pooled for reporting.

## **7.4. Handling of Missing Data and Dropouts**

Handling of dropouts and missing data will depend on their frequency and the nature of the outcome measure.

When calculating rates of adverse events, missing and partial dates will be handled as follows. If the entire adverse event start date is missing then the procedure date will be used for the start date. If the month and the day of the month are missing but the year is available and the year is the same as the year of the procedure then the procedure date will be used for the start date. If the year is greater than the year of the procedure then January 1st will be used for the month and day of the start date. If the day is missing, but the month and year are available, then the 1st will be used as the day of the start date unless the imputed date would be before the procedure in which case the procedure date will be used for the start date of the adverse event.

For baseline categorical variables, "unknown" responses will be counted as not having the characteristic and will be included in the denominator. Missing values will not be counted in rate denominators.

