6.5 Demographics and Other Subject Characteristics

Subject demographics and pre-treatment characteristics will be summarized for the ITT population.

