## **7.6. Demographic and Other Baseline Characteristics**

Continuous variables will be summarized with number of subjects (n), mean, standard deviation, median, and ranges. The frequency distributions (counts and percentages) will be given for categorical data.

This document is electronically controlled. Printed copies are considered uncontrolled.

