### **7.6.2. Smoking History**

The following smoking history data will be summarized:

- History of tobacco use (Yes/No, if yes, current/former)
- Tobacco use: type of tobacco, duration of use, # of units, and use frequencies

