### **7.6.4. Medical History**

The following medical history data will be summarized:

- Has the patient ever had surgery in the thoracic space? (unrelated to Lung Cancer treatment)
- Previous lung disease diagnosis

This document is electronically controlled. Printed copies are considered uncontrolled.

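### Counting baseline 'unknown' answers as 'no' can understate a reported baseline percentage; show them as their own category

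*SAP*

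**What the plan says.** Protocol section 6.8 leaves the missing-data rules to the SAP, so SAP section 7.4 governs. For baseline categorical variables it states that unknown "responses will be counted as not having the characteristic and will be included in the denominator". The next sentence reads: "Missing values will not be counted in rate denominators". No reason is given for treating the two differently.

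Baseline variables are reported descriptively. SAP section 7.6 says: "The frequency distributions (counts and percentages) will be given for categorical data". Protocol section 6.5 (Demographics and Other Subject Characteristics) sets the population: "Subject demographics and pre-treatment characteristics will be summarized for the ITT population". The variables that could fall under the rule include "History of tobacco use" in SAP section 7.6.2 and "Previous lung disease diagnosis" in SAP section 7.6.4. The SAP does not show whether the form offers 'unknown' for these items.

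On size, SAP section 6 says: "Up to 30 subjects who are scheduled for resection of metastatic or primary lung tumor(s) will be enrolled".

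**The concern.** This is an explicit instruction, not an omission, and a programmer who follows it will turn an unestablished status into a negative finding. Two subjects about whom nothing more is known can then move the same percentage differently. The one recorded as 'unknown' enters the denominator as a 'no', and the one left blank drops out.

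What is at stake is the accuracy of the baseline table. Smoking and lung disease history help a reader of a small single-arm study judge to whom the results apply. If unknowns are folded into 'no', the reader cannot tell how many of the negatives were established.

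**Working it through.** The documents state no baseline prevalence and no number of unknown or missing answers, so there is no figure of the plan's own to reproduce. The check is algebra from the SAP 7.4 rule, with assumed counts.

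**Notation.** Y = yes, K = known no, U = unknown, M = missing, and q = the share of unknown subjects who truly have the characteristic.

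**Effect of recoding unknowns, among non-missing subjects.**

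- Reported under SAP 7.4: Y / (Y + K + U)
- True: (Y + qU) / (Y + K + U)
- Error, reported minus true: −qU / (Y + K + U)

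The error is never positive. It is zero if U = 0 or q = 0.

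**Size.** Assume 30 subjects (the SAP maximum) and M = 0. The understatement is then q × U / 30. In the first three rows q is set equal to the prevalence among subjects with a known answer; the last row is the extreme in which every unknown has the characteristic.

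| Assumed q | U = 0 | U = 1 | U = 3 | U = 6 |
|---|---|---|---|---|
| 20% | 0 | 0.7 | 2.0 | 4.0 |
| 50% | 0 | 1.7 | 5.0 | 10.0 |
| 80% | 0 | 2.7 | 8.0 | 16.0 |
| 100% | 0 | 3.3 | 10.0 | 20.0 |

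Entries are percentage points. For the 50% row with U = 6: 24 subjects are known, 12 of them yes; the SAP rule reports 12/30 = 40.0%, the truth is (12 + 0.5 × 6)/30 = 50.0%, and the shortfall is 10.0 points. Where the assumed prevalence does not give whole subjects, the entry is an expected value.

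**Effect of leaving out missing values, relative to all 30 subjects.** The true prevalence lies between Y/30 (no unknown or missing subject has the characteristic) and (Y + U + M)/30 (all of them do).

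- Y = 10, K = 15, U = 0, M = 5: reported 10/25 = 40.0%. The truth lies between 10/30 = 33.3% and 15/30 = 50.0%, so the error lies between +6.7 and −10.0 points.
- Y = 10, K = 15, U = 2, M = 3: reported 10/27 = 37.0%. The truth again lies between 33.3% and 50.0%, so the error lies between +3.7 and −13.0 points.

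Only the recoding of unknowns has a fixed direction. Excluding missing values can err either way, and so can the two rules together when judged against all enrolled subjects.

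**Reach.** The primary endpoint (SAP section 7.9.1) is percentage change between predicted and actual ablation zone measurements. The secondary endpoint is the histology classification. Neither calculation uses the baseline 'unknown' rule, and SAP section 7.5 says that neither endpoint is tested.

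**The case against.** The strongest reply is that the rule may never operate. SAP section 7.6.2 lists the tobacco item as "History of tobacco use (Yes/No, if yes, current/former", and the medical history items in section 7.6.4 show no 'unknown' option. Subjects are surgical candidates whose history is taken at screening, and Protocol section 13.2 makes all eCRF items required and has discrepancies queried. Few unknowns are plausible, and with 30 non-missing subjects a single one moves a percentage by at most 1/30 = 3.3 points. This stands as a limit on size. It does not justify the instruction, which matters only when unknowns do occur.

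A second reply is that 'unknown' is a recorded response while a blank is an uncollected field, which Protocol section 13.2 treats as a deviation unless otherwise specified. Handling them separately is therefore defensible. That stands too, but it supports showing them separately, not scoring one of them as 'no'.

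A third is that percentages among known answers are not the truth either, because they assume the unknowns resemble the knowns. If 'unknown' mostly means that no such history was on record, 'no' may be nearer the mark. This is correct, and it is why the table above varies q and includes zero unknowns.

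**Conclusion.** The point holds in a limited form and is minor. As written, SAP 7.4 can only lower a baseline prevalence among non-missing subjects or leave it unchanged. Under the assumptions of 30 subjects, none missing, and 50% prevalence among known and unknown alike, the understatement is 0, 1.7, 5.0 and 10.0 points for 0, 1, 3 and 6 unknowns. Those counts are illustrations; nothing in the documents says how many unknowns to expect.

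A reader might infer three stronger conclusions that the documents do not support:

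- That the baseline percentages are biased downward as a matter of course, or that the cohort will look healthier than it is. This depends on unknowns occurring and on some of them having the characteristic, and neither is established.
- That dropping missing values adds to the downward error. It has no fixed direction.
- That comparisons or study conclusions are compromised. Neither document plans a comparison with another cohort, and neither endpoint uses the rule.

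**What to change.** Replace the sentence on 'unknown' responses in SAP section 7.4 so that 'unknown' is reported as its own category with its count and is not recoded to 'no'. Report the number missing for each variable, and show the denominator used. If percentages among known answers are also given, label them as such and note that they assume the unknowns resemble the knowns.

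No new data are needed, and readers can recover any other percentage from the counts. The cost is a one-sentence SAP edit, some extra table rows, and denominators that differ between variables.
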